### **8.2. Subject Exclusion Criteria**

Subjects are excluded from this study if any 1 or more of the following criteria is met:

1. Females who are nursing, pregnant, or planning to become pregnant for the duration of the study and up to 30 days after the last application of study medication
2. Clinical diagnosis of alopecia areata or other non-AGA forms of alopecia.
3. Scalp hair loss on the treatment area, due to disease, injury or medical therapy.

4. Active skin disease on the scalp (such as psoriasis or seborrheic dermatitis) or a history of skin disease on the scalp that in the opinion of the investigator would interfere with the study assessments of efficacy or safety.
5. Evidence of hypogonadism defined as serum testosterone < 250ng/dl and/or LH>20mU/ml in males.
6. Active unstable thyroid disease, including subjects on therapy for either hyperthyroidism or hypothyroidism unless their dose of thyroid medication has been stable for 3 months prior to V2 and serum TSH is normal.
7. Subjects with non-pigmented hair.
8. Subjects unable to comply with the following required washout periods:
  - Scalp promoting hair growth products (e.g. minoxidil, finasteride, dutasteride, saw palmetto) for 6 months prior to Visit 2.
  - Anti-androgenetic therapies (e.g. spironolactone, ketoconazole, flutamide, cyproterone acetate) for 6 months prior to Visit 2.
  - Hair transplantation or hair weaving within 6 months of Visit 2
  - Anabolic steroids for 6 weeks prior to Visit 2.
  - Oral or topical JAK inhibitors 3 months prior to Visit 2
  - Platelet rich plasma treatment within 6 months of Visit 2
  - Hair Laser, light or energy treatments to the target hair area within 3 months of Visit 2.
  - Systemic steroids for more than 14 consecutive days in the 2 months prior to Visit 2.
  - Chemotherapy or cytotoxic agents within 12 months of Visit 2.
  - No prior radiation to the scalp.
9. History of, current or suspected systemic or cutaneous malignancy and /or lymphoproliferative disease, other than subjects with: a history of adequately treated and well healed and completely cleared non-melanoma skin cancers (basal or squamous cell carcinoma) treated successfully with no evidence of disease.
10. History of human immunodeficiency virus (HIV), hepatitis B or C.
11. Current herpes zoster infection.
12. Evidence of active, latent or inadequately treated Mycobacterium tuberculosis infection, or history of incompletely treated or untreated tuberculosis. Subjects who have successfully completed therapy for latent tuberculosis may participate.
13. History of serious local infection (e.g., cellulitis, abscess) or systemic infection including but not limited to a history of treated infection (e.g., pneumonia, septicemia) within 3 months prior to Visit 1. Subjects on an antibiotic for a non-serious, acute local infection must complete the course prior to enrollment into the study.
14. Participation in an investigational drug, device, or biologic trial in which administration of an investigational drug, device, or biologic within 30 days or 5 half-lives (whichever is longer) of Visit 2. Subjects who have participated in a study of an investigational drug, device or biologic agent for androgenetic alopecia within 1 year of screening will be eligible to participate only with individual permission from the Medical Monitor.
15. Sensitivity to any of the ingredients in the study medications.
16. Screening ECG findings of:
  - QTcF >450msec for males or >470msec for females (use of the ECG algorithm is acceptable for this purpose)
  - Heart rate < 45 or > 100 beats/minutes (inclusive)

- Rhythm disturbance other than sinus arrhythmia or ectopic supraventricular rhythm (ectopic atrial rhythm)
- Conduction disturbance including PR >240msec, pre-excitation (delta wave and PR <120msec), second degree or higher AV block
- Acute or chronic signs of ischemia
- Left Bundle Branch Block
- Prior myocardial infarction

### **8.3. Subject Withdrawal Criteria**

Subjects will be informed that they are free to withdraw from the study at any time and for any reason. The investigator may remove a subject from the study if, in the investigator's opinion, it is not in the best interest of the subject to continue the study. Examples of other reasons subjects may be discontinued from the study are: a change in compliance with an inclusion or exclusion criteria, occurrence of AEs, occurrence of pregnancy, use of a prohibited therapy or subject is unwilling or refuses to continue with the protocol defined procedures, treatments and/or study visits and/or subject withdraws consent.

Subjects will be permanently discontinued from the study in the event of any of the following:

- Severe infection requiring parental antimicrobial therapy or hospitalization
- Symptomatic herpes zoster
- Malignancy – except for non-melanoma skin cancer (SCC or BCC) not in or near the treatment area
- Anaphylactic or severe allergic reaction
- WBC Count: < 1 x 10^9/L or second occurrence of < 2 x 10^9/L
- ANC:<0.5 x 10^9/L or second occurrence of < 1 x 10^9/L
- Lymphocyte count: < 0.3 x 10^9/L or second occurrence of < 0.5 x 10^9/L
- Platelet count: < 50 x 10^9/L or second event of < 75 x 10^9/L - in each case, value should be confirmed by retesting before treatment discontinuation
- Hemoglobin: < 6.5 g/dL or second occurrence of < 8 g/dL - in each case, value should be confirmed by retesting before treatment discontinuation
- AST or ALT:
  - > 5 x ULN persisting for 2-weeks of study medication interruption or second event of > 5 x ULN
  - 3 x ULN with total bilirubin >2 x ULN or symptoms of hepatocellular injury (fatigue, nausea, vomiting, right upper quadrant pain or tenderness, fever, rash and/ or eosinophilia (>5%).
- Any subject who develops any of the following ECG findings during the active treatment phase will be instructed to stop study medication and will be withdrawn from the study:
  - Clinically significant rhythm disturbance other than sinus rhythm or ectopic supraventricular rhythm (ectopic atrial rhythm)
  - Clinically significant conduction disturbance including PR >240msec, pre-excitation (delta wave and PR <120msec), second degree or higher AV block

- New finding of QRS>120ms (if not present at screen. For example, subjects with Right Bundle Branch Block at screening would not need to be withdrawn from the study if their subsequent ECGs remained unchanged).
- Evidence of QT-interval prolongation, defined as an increase in the QTcF interval>60ms from Visit 1
- Acute signs of ischemia or infarction
- Any ECG abnormality which may, in the opinion of the investigator, represent a new medical issue of concern

A subject that experiences any of the above events must be discontinued from study medication treatment, the site staff must inform the Aclaris medical monitor of the event, and the site staff must perform protocol-required procedures for trial discontinuation and follow-up.

## **9. TREATMENT OF SUBJECTS**

### **9.1. Hair Care During Study**

Subjects enrolled to the study must agree to use the same shampoo/conditioner through the course of the protocol therapy. This information will be documented in the source notes and captured in the subject's CRF. Shampoo/Conditioner must not contain biotin, saw palmetto or tea tree oil (melaleuca oil). Study medication must be applied to a dry scalp. Subjects should not wash their hair for 6 hours after application of study medication. Subjects are required to maintain the same hair style while on study.

### **9.2. Target Area Hair Identification**

In order to assess the efficacy of the study medication, a 1 cm^2 area of the subject's scalp will be identified and be used to count the number of hair follicles that appear in the area throughout the duration of the study treatment period.

Using the Canfield supplied clear plastic template, a 1 cm^2 area will be identified in an actively balding area. The hair will be pulled through the circular area of the plastic template and then the hair will be clipped short using the supplied electric hair clippers. After the hair is clipped, the template is to be removed and the hairs are to be further trimmed to approximately 1mm in length using 4- inch curved scissors. Once the target area is identified and the hair is clipped then a small tattoo will be applied to mark the target area. Refer to [Section 9.4](#) regarding the procedure for the scalp tattoo. This target area will be used for each TAHC/TAHW assessment throughout the study.

**Figure 1: Target Area Identification**

### **9.3. Preparation of Subjects Scalp for Global and Macro Photographs**

Investigational sites are to perform the global photographs prior to performing the macro photographs.

For all vertex global scalp photographs (male subjects only), the subject's hair is to be combed outwards from the vertex like the spokes of a wheel. For all frontal global scalp photographs

(male and female subjects), the subject's hair is to be parted in the center and the hair is to be combed away from the center part.

The global photographs will be used by the investigator to perform the Investigative Global Assessment (IGA) and by subject to perform the Subject Self-Assessment (SSA). Refer to Section [11.3](#).

#### **9.4. Scalp Tattoo**

At Visit 2 all subjects will be required to have a permanent dot tattoo applied to their scalp in an actively balding area. The tattoo will mark the center of the identified target area from which the macro photographs and TAHC and TAHW will be performed.

All sites will be supplied with a tattoo machine and the necessary ink to apply the tattoo. The tattoo machines will be supplied by Canfield and sites will be provided with instructions on how to prepare the machine and the subject's scalp to ensure that the tattoo is applied appropriately.

#### **9.5. Application of Study Medication**

Subjects will be instructed to apply a thin film of ATI-50002 Topical Solution 0.46% (up to 4-mL), twice-daily; once in the morning and approximately 12 hours later to the balding area of the clean dry scalp. Refer to [Appendix 1](#) for the complete application instructions. The subject must wash her/his hands thoroughly before and after each study drug application. Investigational site staff will dispense a month's supply of study medication along with disposable droppers to the subject at each study visit. Study medication bottles will be weighed by the site staff at the time of dispensing and when the bottles are returned. Subjects are to return used and unused study medication at each study visit. The disposable droppers should be disposed of at the subject's home.

At each study visit, the study staff will review the study medication instructions and proper application technique. ([Appendix 1](#)) with the subject. During Visit 2, the subject will apply the first dose of study medication in the office under the instruction and supervision of the study staff.

During each site visit, the study staff member will:

- Dispense study medication bottles to the subject.
- Instruct the subject on the appropriate application technique following instructions in [Appendix 1](#).
- Weigh the bottles prior to dispensing the study medication
- Observe the subject's first study medication application to ensure proper coverage and monitor the subject for at least 20 minutes (Visit 2 only).

All used study medication bottles will be weighed by the investigational site at each visit.

## 9.6. Concomitant Medications

Concomitant therapies are any new or existing therapy received from Visit 1 until discharge from the study.

Concomitant therapies include drug (*e.g.*, prescription, over-the-counter [OTC]) and non-drug (*e.g.*, chiropractic, physical therapy, energy-based treatments) therapies. Subjects will refrain from receipt of any therapy in compliance with the inclusion/exclusion criteria. Subjects should refrain from changing the use of any concomitant therapies during the study.

All new or modified concomitant therapies used during the study must be recorded in the subject's eCRF.

## 9.7. Prohibited Medications

The following medications will be prohibited from being used while the subject is on study and for the identified time-frame prior to Visit 2:

- Scalp hair growth promoting products (*e.g.* minoxidil, finasteride, dutasteride, saw palmetto) for 6 months prior to Visit 2.
- Anti-androgenetic therapies (*e.g.* spironolactone, flutamide, cyproterone acetate) for 6 months prior to Visit 2.
- Hair transplantation or hair weaving within 6 months of Visit 2.
- Semi-permanent hair products (*e.g.* texturizers, relaxers) for 30 days prior to Visit 2.
- Anabolic steroids for 6 weeks prior to Visit 2.
- Oral and topical JAK inhibitors for 3 months prior to Visit 2.
- Medicated shampoo or conditioner containing biotin, saw palmetto or tea tree oil (*melaleuca* oil) for 30 days prior to Visit 2.
- Platelet rich plasma treatment within 6 months of Visit 2.
- Hair Laser, light or energy treatments to the target hair area within 3 months of Visit 2.
- Systemic steroids for more than 14 consecutive days in the 2 months prior to Visit 2
- Chemotherapy, cytotoxic agents or within 12 months of Visit 2.
- Prior radiation to the scalp.

## 9.8. Treatment Compliance

The investigator or designee will be responsible for monitoring subject compliance through questioning the subject, documenting missed doses, if any, weighing the bottle before dispensing and after return and visual inspection of the quantity in the study medication bottles (used and unused). Study staff will counsel the subjects, as required to make sure subjects are compliant with study medication applications.

## 9.9. Study Medication Interruption

Treatment with ATI-50002 Topical Solution should be temporarily interrupted in the event of severe adverse events considered related to ATI-50002, or in the event of one or more of the abnormal laboratory values in [Table 4](#).

**Table 4: Study Medication Interruption Criteria**

Laboratory Test	Hold Study Medication if:	Resume Study Medication if:
WBC count	< 2 x 10  /L	≥ 2.5 x 10  /L
ANC	< 1 x 10  /L	≥ 1.5 x 10  /L
Lymphocyte count	< 0.5 x 10  /L	≥ 0.75 x 10  /L
Platelet count	< 75 x 10  /L	≥ 100 x 10  /L
Hemoglobin	< 8 g/dL or a decrease > 2g/dL	≥ 10 g/dL
AST or ALT	> 3 x ULN	< 2 x ULN or within 20% of Baseline values
Serum creatinine	>2 x ULN	<1.5 x ULN or within 10% of Baseline value

If a subject has one or more of the abnormal laboratory values noted in [Table 4](#), the investigator or designee upon receipt and review of the central laboratory report should instruct the subject to hold study medication applications. The investigator or designee should ask the subject about symptoms, concomitant illnesses and medications and repeat the test(s) as soon as possible. The Medical Monitor must be notified of dose interruptions due to SAEs considered related to study medication or laboratory abnormalities noted in [Table 4](#).

If the retest confirms the abnormal laboratory value, then the study medication should continue to be held followed by repeat testing once a week or sooner at the discretion of the investigator. The subject should be followed until the laboratory abnormality(s) return to normal or to baseline values.

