## 7.5. Schedule of Assessments

**Table 2: Schedule of Assessments-Initial 26 weeks of Treatment**

	Screening	Baseline	Treatment								Follow up Safety/Early Termination Visit 
	Visit 1	Visit 2	Visit 3	Visit 4	Visit 5	Visit 6	Visit 7	Visit 8	Visit 9	Visit 10	
			Week 3	Week 4	Week 8	Week 12	Week 16	Week 20	Week 24	Week 26	4 weeks post last application of ATI-50002
Treatment Day	-14 to 0	1	21	28	56	84	112	140	168	182	
Visit Windows	N/A	N/A	+/- 3 days	+/-4 days	+7 days	+/-7 days	+7 days	+/-7 days	+/-7 days	+7 days	+7 days
Informed Consent 	X										
Inclusion/Exclusion Criteria	X	X									
Demographics and Medical History	X										
Physical Exam 	X										X
Vital Signs 	X	X	X	X	X	X	X	X	X	X	X
Fitzpatrick Skin Type	X										
Prior Hair Treatment Assessment 	X										

	Screening	Baseline	Treatment								Follow up Safety/Early Termination Visit 
	Visit 1	Visit 2	Visit 3	Visit 4	Visit 5	Visit 6	Visit 7	Visit 8	Visit 9	Visit 10	
			Week 3	Week 4	Week 8	Week 12	Week 16	Week 20	Week 24	Week 26	4 weeks post last application of ATI-50002
Treatment Day	-14 to 0	1	21	28	56	84	112	140	168	182	
Visit Windows	N/A	N/A	+/- 3 days	+/-4 days	+7 days	+/-7 days	+7 days	+/-7 days	+/-7 days	+7 days	+7 days
Clinical Chemistry and CBC 	X				X		X		X	X	X
Quantiferon Gold 	X										
Total Iron Binding Capacity (TBIC), Serum Iron, Serum Ferritin	X										
Dihydrotestosterone (DHT), Testosterone, Estrogen, DHEA	X				X		X		X	X	X
Urine Pregnancy Test		X		X	X	X	X	X	X	X	X
Serum Pregnancy	X										
Serum PSA	X										
Thyroid Panel	X										
ECG	X			X						X	X

	Screening	Baseline	Treatment								Follow up Safety/Early Termination Visit 
	Visit 1	Visit 2	Visit 3	Visit 4	Visit 5	Visit 6	Visit 7	Visit 8	Visit 9	Visit 10	
			Week 3	Week 4	Week 8	Week 12	Week 16	Week 20	Week 24	Week 26	4 weeks post last application of ATI-50002
Treatment Day	-14 to 0	1	21	28	56	84	112	140	168	182	
Visit Windows	N/A	N/A	+/- 3 days	+/-4 days	+7 days	+/-7 days	+7 days	+/-7 days	+/-7 days	+7 days	+7 days
Norwood-Hamilton classification(males); Sinclair Scale (females)Assessment	X	X					X			X	X
Target Area Hair Identification and Tattoo application 		X									
Global Scalp Photograph 	X	X 			X 		X 			X 	X
Macro Scalp Photographs 		X			X		X			X	

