### 12.1.7. Laboratory Assessments

#### 12.1.7.1. Clinical Chemistry/Hematology

All subjects are required to have a blood chemistry panel performed at Visit 1 (Screening), Visit 5 (Day 56), Visit 7 (Day 112), Visit 9 (Day 168), Visit 10 (Day 182) and Visit 11 (Day 210) /Safety Follow up Visit. A qualified staff member will collect non-fasting blood samples and ship the samples to a central laboratory for analysis. The following tests will be performed:

Chemistry Panel	Complete Blood Count
Albumin	Hematocrit
Alkaline phosphatase	Hemoglobin
Alanine aminotransferase (ALT)	Platelet count
Aspartate aminotransferase (AST)	Red blood cell morphology
Blood urea nitrogen (BUN)	Red blood cell count
Bicarbonate	White blood cell count
CPK	
Calcium	White blood cell differential
Chloride	% & absolute
Creatinine	Basophils
Glucose	Eosinophils
Lactate dehydrogenase (LDH)	Lymphocytes
Phosphorus	Monocytes
Potassium	Neutrophils
Sodium	
Total bilirubin	
Total protein	

Uric Acid  
Total cholesterol, LDL, HDL  
Triglycerides  
Total Iron Binding Capacity (TIBC) (Visit 1 only)  
Serum iron (Visit 1 only)  
Serum Ferritin (Visit 1 only)  
Testosterone  
Estrogen  
DHEA  
Dihydrotestosterone (DHT)  
Serum PSA (males only; Visit 1 only)  
Lutenizing Hormone (LH) (Visit 1 only)  
Thyroid Panel (Visit 1 only) (including TSH, Total T4,  
Total T3, Free T4, Free T3, Reverse T3 (rT3), T3U,  
Free T4 Index, and TPO and AntiTG antibodies)

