Appendix 16.2.3.9 Clinical Laboratory Assessments: Hematology

Group: Female, Male

Patient	Age (years)	Gender	Parameter (unit)	Visit	Study Day ^a	Value	Normal Range		List Criteria Met, if applicable, for Hold of Study Medication
xx-xxx	60	Female	Hemoglobin (g/dL)		-10 -1 ^b 28 38	XXX XXX XXX XXX	XX.X-XX.X	L H	< 8 g/dL or decrease > 2 g/dL
			Hematocrit (%)						

^a Assessment Date – Date of First Application (+1 if ≥ first application of study medication).

PROGRAMMING NOTE: Sort by group, patient, parameter, and study day. For criteria for holding study medication see protocol – Section 10.2.4.1

	Repeat format for:
Appendix 16.2.3.10	Clinical Laboratory Assessments: Biochemistry
Appendix 16.2.3.11	Clinical Laboratory Assessments: Hormones

^b Value used for baseline.

23 Apr 2019 Statistical Analysis Plan

Protocol: ATI-50002-AGA-201

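### The platelet entry limit, which also carries a unit error, admits subjects below the hold limit, and a haemoglobin fall can meet the hold and resume limits of Table 4 on the same result

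*Protocol*

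**What the plan says.** **Platelets.** Inclusion criterion 8 (Protocol Synopsis and Section 8.1) requires a platelet count above 50,000 per mL and, in the same line, an ANC above 1,000 per mm^3. Table 4 in Section 9.9 holds study medication for platelets below 75 x 10^9/L and resumes at 100 x 10^9/L or more. Section 8.3 stops treatment permanently for "Platelet count: < 50 x 10 9 /L or second event of < 75 x 10 9 /L", after a confirming retest.

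**Haemoglobin.** Table 4 holds for "< 8 g/dL or a decrease > 2g/dL" and resumes at 10 g/dL or more. The AST/ALT and creatinine rows give a Baseline-relative alternative for resuming; the haemoglobin row does not. Below the table, Section 9.9 says "If the retest confirms the abnormal laboratory value, then the study medication should continue to be held", with repeat testing at least weekly, and "The subject should be followed until the laboratory abnormality(s) return to normal or to baseline values". Section 8.3 stops permanently on absolute values only: "Hemoglobin: < 6.5 g/dL or second occurrence of < 8 g/dL".

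**Testing schedule.** The row "Clinical Chemistry and CBC" in Protocol Table 2 is marked at Visit 1 (Day -14 to 0) and next at Visit 5 (Day 56, window printed as +7 days). Section 12.1.7.1 gives the same visits.

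**SAP.** The haematology listing (Appendix 16.2.3.9) shows the hold criterion as "< 8 g/dL or decrease > 2 g/dL" and sends the programmer to protocol Section 10.2.4.1. Protocol Section 10 covers drug supply, runs from 10.1 to 10.4 and has no such subsection.

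**The concern.** These lines tell sites whom they may enrol, when to interrupt dosing and when to restart. Safety is part of the primary objective, so the lines should agree with each other.

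For platelets, a subject with a stable count of 60 x 10^9/L passes screening and starts treatment at a count that would interrupt it in someone already on drug. Once tested on treatment, the same unchanged count triggers a hold, and restarting needs 100 x 10^9/L, a level never required at entry. A second result below 75 then ends participation. In a single-arm study, that hold or stop would reflect the entry rule rather than the drug.

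For haemoglobin, one result can satisfy both the hold column and the resume column. A site that reads only the resume column could restart a subject at 12.0 g/dL after a fall from 14.5, although the subject is still 2.5 g/dL down. Section 8.3 offers no numeric rule for a fall that stays at 8 g/dL or above, so this Table 4 row is the only one that applies.

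**Working it through.** The plan gives no derived figure to reproduce. The inputs are the limits and visit days above. Haemoglobin Baselines are assumed, because the documents give none.

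**Platelet units**
- As printed: 50,000 per mL x 1,000 mL/L = 5 x 10^7/L = 0.05 x 10^9/L.
- Read as per mm^3 (an inference from the ANC unit in the same criterion): 50,000 x 10^6 = 50 x 10^9/L.
- Against the hold limit: 75 - 0.05 = 74.95 below, or 75 - 50 = 25 below (x 10^9/L). Entry lies below hold under both readings.
- Against the permanent-stop limit: 0.05/50 = 1/1000 as printed; 50 - 50 = 0 under the inferred unit.
- ANC for comparison: 1,000 x 10^6 = 1 x 10^9/L, exactly its Table 4 hold limit.

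**Dosing before the next scheduled count**
- First application Day 1, next count Day 56: 56 - 1 = 55 days.
- With the +7 day window: 63 - 1 = 62 days.

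**Haemoglobin, current rule.** Take the decrease as measured from Baseline B.
- Hold if Hb < H, where H = max(8, B - 2).
- Resume if Hb >= 10.
- Both hold when 10 <= Hb < B - 2, a band of width max(0, B - 12).

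**Haemoglobin, revised rule.** H is unchanged. The resume limit is R = max(10, B - 2) for B >= 10, and R = B for 8 <= B < 10.

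| Baseline B (g/dL) | H | Overlap now | R revised | R - H |
|---|---|---|---|---|
| 8 | 8 | 0 | 8 | 0 |
| 9 | 8 | 0 | 9 | 1 |
| 10 | 8 | 0 | 10 | 2 |
| 11 | 9 | 0 | 10 | 1 |
| 12 | 10 | 0 | 10 | 0 |
| 13 | 11 | 1 | 11 | 0 |
| 14 | 12 | 2 | 12 | 0 |
| 14.5 | 12.5 | 2.5 | 12.5 | 0 |
| 15 | 13 | 3 | 13 | 0 |
| 16 | 14 | 4 | 14 | 0 |

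R is never below H, so no value meets both revised columns. For B of 12 or more the two limits touch without a buffer. A tighter margin m < 2 in the resume rule would open a gap of 2 - m there. The current rule also has a fault at the low end: with B below 10, a held subject who returns fully to Baseline still cannot resume.

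**The case against.** The strongest reply concerns haemoglobin. A value still more than 2 g/dL down is itself one of the abnormal values in Table 4. The text directly below the table keeps it on hold once confirmed, requires retesting at least weekly, and requires that the Medical Monitor be told. Restarting at 12.0 after 14.5 would ignore that paragraph. This stands as a limit on the harm, and a reader who inferred that the protocol as a whole directs such a restart would go too far. It does not remove the fault: the resume column is the only place that gives a numeric restart limit, and it contradicts the sentence beneath it. The follow-up sentence says how long to monitor, not when to restart.

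The missing reference for the decrease can also be read charitably. Neighbouring rows of Table 4 name Baseline, and the SAP listing marks the value used for baseline. Part of the SAP is not available here, so an earlier definition cannot be ruled out. Baseline is the natural reading; the row should say so.

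On platelets, a reader might infer that the entry limit as printed equals the permanent-stop limit. It does not: equality depends on replacing the printed unit. That replacement is very likely right, but it remains an inference. What needs no inference is that entry lies below hold.

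A reader might also count 56 to 77 days between screening and the next scheduled count and call it exposure. That span includes up to 14 days before dosing; exposure is about 55 to 62 days.

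Finally, subjects are aged 18 to 50, most malignancy and recent chemotherapy are excluded, and the investigator may withdraw a subject at any time. Low platelet counts should therefore be uncommon, which bears on severity.

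**Conclusion.** The point holds and is minor. Two sets of stated rules conflict when followed.

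- The platelet entry limit has a unit error. Under either unit it admits subjects below the hold limit, by 25 x 10^9/L if the intended limit is 50.
- The haemoglobin hold and resume columns overlap by Baseline minus 12 g/dL for every Baseline above 12, taking Baseline as the reference for the decrease.

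The documents do not support reading this as a serious hazard. Existing retest, hold and notification rules limit the harm, few of the 24 subjects are likely to be affected (the number cannot be estimated from the documents), and efficacy results do not change. The wrong section pointer in the SAP is clerical.

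**What to change.** - **Inclusion criterion 8 (Synopsis and Section 8.1):** state the platelet limit as >= 75 x 10^9/L, matching the hold limit as the ANC limit does. Cost: a rare subject is excluded. The documents do not show whether enrolment has closed; if it has, this change has little effect in this trial.
- **Table 4, haemoglobin row:** hold if below 8 g/dL or if the decrease from Baseline exceeds 2 g/dL. Resume if at least 10 g/dL and no longer more than 2 g/dL below Baseline. When Baseline is 8 to below 10 g/dL, return to Baseline is sufficient. The medical monitor may set a tighter margin; the documents give no basis for choosing one. A Baseline below 8 already meets the hold column and needs a medical monitor decision. Cost: some holds last longer, with added unscheduled weekly retests and lost dosing time.
- **SAP Appendix 16.2.3.9 (editorial):** add that the decrease is from Baseline, and change the pointer to protocol Section 9.9, Table 4.

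In all, this is one criterion in two places, one table row and one SAP listing, with no new scheduled visits or tests.
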